8.2. Clinical Laboratory Analyses

Laboratory evaluations will be based on GSK Core Data Standards and will include:

- Hematology laboratory tests
- Chemistry laboratory tests
- Urinalysis
- Other screening tests

Details of the planned displays are presented in [Appendix 11](#).

The laboratory assessments for each category are displayed in [Table 2](#).

Table 2 Laboratory Assessments

Laboratory Assessments	Parameters						
Hematology	Platelet Count		RBC Indices: MCV MCH %Reticulocytes	WBC count with Differential: Neutrophils Lymphocytes Monocytes Eosinophils Basophils			
	RBC Count						
	Hemoglobin						
	Hematocrit						
Clinical Chemistry ^{1,2,3}	BUN	Potassium	Aspartate Aminotransferase (AST)/ Serum Glutamic-Oxaloacetic Transaminase (SGOT)		Total and direct bilirubin		
	Creatinine	Sodium	Alanine Aminotransferase (ALT)/ Serum Glutamic-Pyruvic Transaminase (SGPT)		Total Protein		
	Glucose (non-fasting)	Calcium	Alkaline phosphatase		² Cardiac troponin T ³ NT-proBNP		
Routine Urinalysis ¹	Specific gravity pH, glucose, protein, blood, ketones, bilirubin, urobilinogen, nitrite, leukocyte esterase by dipstick Microscopic examination and laboratory quantification of proteinuria (if blood or protein is abnormal on dipstick) Part B: Alcohol						
Combined throat and nasopharyngeal swab	COVID-19 (SARS-CoV2) (see SRM for further details)						
Other Screening Tests	Blood (serum): Follicle-stimulating hormone and estradiol (as needed in women of non-childbearing potential only) Serology (TB test, HIV antibody, HBsAg, HBcAb and hepatitis C virus antibody) QuantiFERON test Complement protein C3 and C4 Urine: Urine drug screen to include at minimum: amphetamines, barbiturates, cocaine, opiates, cannabinoids and benzodiazepines. Urine albumin-creatinine ratio (UACR)						

Notes

1. Details of liver chemistry stopping criteria and required actions and follow-up assessments after liver stopping or monitoring event are given in Protocol Section 7.2.1 and Appendix 6a and 6b of protocol. All events of ALT $\geq 3 \times$ upper limit of normal (ULN) and bilirubin $\geq 2 \times$ ULN ($> 35\%$ direct bilirubin) or ALT $\geq 3 \times$ ULN and international normalized ratio (INR) > 1.5 , if INR measured, which

may indicate severe liver injury (possible Hy's Law), must be reported as an SAE (excluding studies of hepatic impairment or cirrhosis).

2.Troponin T using high sensitivity test.

3.NT-proBNP (N-terminal pro B-type natriuretic peptide) at baseline and Day 57 visit only.

Laboratory/analyte results that could unblind the study will not be reported to investigative sites or other blinded personnel until the study has been unblinded.

8.3. Other Safety Analyses

The analyses of non-laboratory safety test results will be based on GSK Core Data Standards, unless otherwise specified.

The non-laboratory safety test results include:

- Vital Signs
- ECGs
- Echocardiogram
- Telemetry (for Part A only)
- Holter monitoring (for Part B only at Screening)

8.4. COVID-19 Pandemic Statistical Displays

A summary of the following COVID-19 assessments may be produced: Case Diagnosis, COVID-19, Test performed, and Results of the COVID-19 test. Additionally, a listing of all subjects with visits and assessments impacted by the pandemic may be produced. The listing will include:

1. Site Identifier
2. Treatment for parallel group studies
3. Unique Subject Identifier
4. Subject Identifier
5. Impacted Visit
6. Impact
7. Reason for Impact

Details of the planned displays are presented in [Appendix 11](#).

9. PHARMACOKINETIC ANALYSES

9.1. Serum Pharmacokinetics

The PK analyses described below will be carried out for GSK3858279 in serum.

9.1.1. Endpoint / Variables

CCI

[figure not shown]

9.1.1.1. Drug Concentration Measures

Refer to [Appendix 5](#)(Section 14.5.3).

9.1.1.2. Derived Pharmacokinetic Parameters

CCI

NOTES:

CCI

9.1.1.2.2. Part B

CCI

NOTES:

Additional parameters may be included as required.

In the event that a robust and predictive population PK/TE model cannot be developed e.g. data limited by high levels of NR data, all parameters listed in the table will be derived directly from the observed data using standard non-compartmental analysis. In such case, PK parameters for subjects on sparse sampling schedule will be only calculated at weeks 1 and 8.

9.1.2. Summary Measure

Individual and mean/median concentration-time profiles of GSK3858279 in serum (stratified by treatment group in Part A) will be plotted and listed. Serum concentrations will be summarized descriptively. Derived serum PK parameters will be summarised using descriptive statistics, graphically presented (where appropriate) and listed.

9.1.3. Population of Interest

The serum pharmacokinetic analyses will be based on the Pharmacokinetic population, unless otherwise specified.

9.1.4. Strategy for Intercurrent (Post-Randomization) Events

Missing data would be considered as Missing at Random and no imputations for missing data would be carried out.

9.1.5. Statistical Analyses / Methods

Details of the planned displays are presented in [Appendix 11](#) and will be based on GSK Data Standards and statistical principles.

Unless otherwise specified, endpoints / variables defined in Section [9.1.1](#) will be summarised using descriptive statistics, graphically presented (where appropriate) and listed.

9.1.5.1. Dose proportionality

Dose proportionality in Part A will be assessed by visual inspection of:

- Dose normalised $AUC(0-\infty)$ [or if not available $AUC(0-t)$] and C_{max} values versus dose.

Dose proportionality may also be assessed using the power model described below.

Dose proportionality
Endpoints
• $AUC(0-t)$, $AUC(0-\infty)$ and C_{max}
Model specification

 • Power model (log-log linear model): $y = \alpha \times dose^\beta \Leftrightarrow \log_e(y) = \log_e(\alpha) + \beta \times \log_e(dose)$ 
Where
 
 ○ y = endpoint of interest ○ $dose$ = actual dose (mg) received under fasted condition ○ β = parameter associated to dose (slope)

- α = subject-specific random effect (intercept)
- Terms fitted in the power model:
 - Response: log transformation of the endpoint of interest $\log_e(y)$
 - Fixed continuous covariates: $\log_e(dose)$
 - Random: subject

Model checking & diagnostics

- Normality assumptions underlying the model used for analysis will be examined by obtaining a normal probability plot of the residuals and a plot of the residuals versus the fitted values (i.e. checking the normality assumption and constant variance assumption of the model, respectively) to gain confidence that the model assumptions are reasonable.
- If there are any departures from the distributional assumptions, alternative models will be explored using appropriate transformed data

Model results presentation

Table of the estimated slopes and 90% CI (slope close to 1 implies dose proportionality)

CCI

CCI

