4. STUDY DESIGN

4.1. Overall Design

This study is a randomized, double-blind, placebo-controlled, two-part trial. A study diagram is included in Figure 1.

Part A is a single ascending dose escalation study to evaluate the safety, tolerability, PK, and target engagement of GSK3858279 in healthy participants. Single IV doses and a single SC dose will be investigated in separate cohorts of participants. Target engagement (CCL17) will be assessed both in blood [CCL17]

(see Section 4.3 and SoA, Section 1.3).

Up to five single ascending IV doses of GSK3858279 will be investigated. A single SC dose of GSK3858279 will also be assessed to determine bioavailability, as future studies as well as the target product will likely involve SC administration.

A Dose Escalation Committee (DEC) will review at least 15 days of safety and PK data prior to progression to the next dose level (see Study Rationale Section 4.3). The decision to progress the SC cohort will be based upon understanding the PK and TE data from some IV cohorts. The decision to progress to Part B dosing in OA participants will be based on the safety, PK and TE data following single IV and single SC administrations in healthy participants.

In Part A, sentinel participants will be used in each dosing cohort: two participants will be dosed first, one will be randomised to GSK3858279 and one to placebo. 48-hour post

dose safety data from the sentinel participants will be reviewed by the investigator and the remainder of the cohort will then be dosed if deemed safe to do so. The dose level investigated in Part B will not exceed the highest dose tested in Part A.

Part B will investigate the safety, tolerability, efficacy (pain), PK, TE and immunogenicity of weekly SC dosing for 8 weeks of GSK3858279 or placebo (in a 1:1 ratio) in participants with OA of the knee.

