4.1.1. Treatment Groups and Duration

The total duration of the study (from signing of the informed consent until final follow-up) for each participant will vary between cohorts (see Table 1). The screening period will be of a maximum of 28 days for all cohorts in Part A and a maximum of 42 days in Part B. Final follow-up visits will be scheduled to occur when approximately 5 half-lives of GSK3858279 have elapsed after dosing. Follow-up visits are scheduled earlier for the lowest dose group where PK parameters are expected to be below the lower limit of quantification (LLQ), and are extended by an additional 4 weeks for the top dose cohort where extended pharmacology may be observed (see Table 1 and Schedule of Activities [SoA, Section 1.3]).

In Part A, each participant will receive a single dose of study intervention (GSK3858279 or placebo), either IV or SC. The planned dosing schedule is described in Table 1, although dose levels are subject to change depending on emerging study data. The maximum dose (level) that may be administered in the study will be 10 mg/kg, both for IV and SC cohorts. See Section 4.4 for further details.

In Part B, each participant will receive SC injections weekly for 8 weeks.

Table 1 Dosing schedule and study duration

Part	Cohort	Dose of GSK3858279	Follow up (days post dosing)	Maximum study duration including screening (days)
Part A	Cohort 1 IV	Up to 0.1 mg/kg	84	112
	Cohort 2 IV	Up to 0.3 mg/kg	112	140
	Cohort 3 IV	Up to 1 mg/kg	112	140
	Cohort 4 IV	Up to 3 mg/kg	112	140
	Cohort 5 IV	Up to 10 mg/kg	140	168
Cohort 6 SC	Between 1 and 3	140	168	
	Colloit 6 SC	mg/kg (max 240 mg)		
Part B	Cohort 7 SC	240 mg	56 (Treatment)	182/183
			84(Follow Up)	

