2.3. Study Design

This study will be a randomized, double-blind, placebo-controlled, two-part trial. A study diagram is included in [Table 1](#).

Part A will be a single ascending dose escalation study to evaluate the safety, tolerability, PK, and target engagement of GSK3858279 in healthy participants. Single IV doses and a single SC dose will be investigated in separate cohorts of participants. Target engagement will be assessed both in blood and [\[CC1\]](#)

[\[CC1\]](#) Up to five single ascending IV dose levels of GSK3858279 will be investigated. A single SC dose of GSK3858279 will also be assessed to determine bioavailability, as future studies as well as the target product will likely involve SC administration.

A Dose Escalation Committee (DEC) will review at least 15 days of safety and PK data prior to progression to the next dose level. The decision to progress the SC cohort will be based upon understanding the PK and TE data from some IV cohorts. Once sufficient safety, PK and target engagement data is collected from the top IV dose and SC cohorts, a data review will take place and a decision to proceed with Part B of the study may be made.

In Part A, sentinel participants will be used in each dosing cohort: two participants will be dosed first, one will be randomized to GSK3858279 and one to placebo. 48-hour post dose safety data from the sentinel participants will be reviewed by the investigator and the remainder of the cohort will then be dosed if deemed safe to do so.

Part B will investigate the safety, tolerability, clinical efficacy on pain (as primary endpoints), PK, target engagement and immunogenicity in participants with OA of the knee after weekly SC dosing for 8 weeks of GSK3858279 or placebo in a 1:1 ratio.

The table below provides an overview of the study design and the key features.

Table 1 Study Design

Study Design	
Figure 1: Parts A and B: Study Design	

Part A Single Ascending Dose - Healthy participants
 
Part B Repeat Dose - Knee OA participants
 
IV: intravenous; N: number of participants; OA: osteoarthritis; PK: pharmacokinetics; SC: subcutaneous
	

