4.1.2. Part A only

Population	Description	Outputs
Blister	
 All participants in the Safety population who had at least one blister assessment. This population will be based on the treatment the participant received. 	
 PD
Blister Pharmacokinetic	
 All participants in the Safety population who had at least 1 reportable blister PK assessment. This population will be based on the treatment the participant received. 	
 PK

CC1	
 • Note: Non-quantifiable [NQ] values will be 	
Fully treated	
 • All participants in the Safety population who received at least 80% of planned study treatment*. • This population will be identified by review of protocol deviations 	
 • PK, PD

*Part A has a single dose. Percentage of actual amount administered will be derived using the planned dose and the injected infusion volume.

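### The optional Part A power model pairs a subject random intercept with a residual, but each subject gives one value per endpoint, so the two variances cannot be separated (low severity)

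*SAP*

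**What the plan says.** **The model.** SAP 9.1.5.1 regresses the log of AUC(0-t), AUC(0-∞) or Cmax on log dose. Log dose is the only fixed covariate listed. Subject is listed as random, and α is described as a "subject-specific random effect (intercept". Dose is the actual amount in mg, qualified as "received under fasted condition". Residuals are to be plotted for normality and against fitted values, and other models may be explored if assumptions fail.

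**The output.** "Table of the estimated slopes and 90% CI (slope close to 1 implies dose proportionality". The section gives no degrees-of-freedom method, no acceptance limits, and no fallback if the covariance model cannot be fitted.

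**Its status.** Visual inspection of dose-normalised values is the stated method. The model is an addition: "Dose proportionality may also be assessed using the power model described below". Protocol 9.1 and SAP 2.4 do plan a dose-proportionality assessment, restricted to single IV dosing, and SAP 14.11.8.1 schedules Table 3.03 for it.

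**The design.** Protocol 4.1.1: "In Part A, each participant will receive a single dose of study intervention (GSK3858279 or placebo), either IV or SC". SAP 4.1.2 agrees: "Part A has a single dose". SAP 2.3: "Single IV doses and a single SC dose will be investigated in separate cohorts of participants". Protocol 4.1: "Up to five single ascending IV doses of GSK3858279 will be investigated". Protocol 9.2.1 puts six participants on active drug at each dose level.

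**The concern.** A subject random intercept is useful when a subject contributes several values, as when one person is measured at several doses. Here it has nothing to work on. With one row per subject, the subject effect and the residual enter each observation in the same way, and the data cannot tell them apart.

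What is at stake is the reproducibility of one table. Two programmers following SAP 9.1.5.1 literally could report different standard errors or degrees of freedom for the same slope, and see different residual plots. SAP 12.1.4.1 shows the contrast. There each subject has repeated visits and sample types, so a random subject effect is meaningful, and the text names Kenward-Roger degrees of freedom and fallback covariance structures. The power model has neither the repeated data nor those instructions.

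**Working it through.** The documents give no precision or power figure for this model, so there is none to reproduce.

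**Inputs from the documents.** Six cohorts × 6 = 36 active and 6 × 2 = 12 placebo, which agrees with Protocol 4.2. Five IV cohorts × 6 = 30 IV-active participants, with one value each per endpoint.

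**Assumptions not in the documents.** Total log-scale SD of 0.2 to 0.4; weights uniform over 50 to 100 kg (the eligibility range in Protocol 5.1); true slope 0.96, close to the 0.957 obtained by regressing log predicted IV AUC on log dose in Protocol Table 2.

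**Step 1: the covariance.** Write log yᵢ = log α + β log doseᵢ + uᵢ + eᵢ, with i = 1 to 30. As each subject has one row, Var(y) = (σ²_u + σ²_e) × I. Only the sum appears. In one simulated data set the REML log-likelihood was 19.2697 at subject shares of 0, 10, 25, 50, 75, 90 and 99% of a fixed total variance. The 2 × 2 information matrix for the two variances has rank 1.

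**Step 2: the slope.** Because Var(y) is a multiple of the identity, generalised least squares equals ordinary least squares. At every split above, the slope was 0.9570 and its SE 0.02914.

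**Step 3: the valid interval.** The total variance is estimated on N - 2 = 28 df, with t(0.95, 28) = 1.701. The 90% interval is 0.957 ± 1.701 × 0.02914 = 0.957 ± 0.050, or 0.91 to 1.01. With five active participants per IV cohort (25 in all), df = 23 and t = 1.714. Over 20,000 simulations per setting with N = 30, coverage was 89.6% to 90.2%, and the mean half-width was:

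| Total log-SD (assumed) | Mean 90% half-width |
|---|---|
| 0.2 | 0.037 |
| 0.3 | 0.056 |
| 0.4 | 0.074 |

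**Step 4: what a literal fit can do.**

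- *Degrees of freedom.* Adding 30 subject columns Z to the 2 fixed columns X gives rank[X Z] = 30, so a rule that subtracts this rank leaves 30 - 30 = 0.
- *Standard error.* Six further simulated data sets were fitted by a mixed-model routine (not SAS) with the redundant term kept. The slope always matched ordinary regression. One optimiser reproduced the SE each time. The other two split the variance 50:50, and in four of the six data sets reported an SE well below the correct one, for example 0.0042 against 0.0296.
- *Residual plots.* If the subject share is f, the predicted subject effect is f × rᵢ, where rᵢ is the ordinary residual. The conditional residual is (1 - f) × rᵢ and the fitted value absorbs the rest. With SD 0.30, the apparent residual SD is 0.5 × 0.30 = 0.15 at f = 50% and 0.1 × 0.30 = 0.03 at f = 90%. In simulation, the mean within-cohort correlation of residual with fitted value was about 0 at f = 0, 0.55 at 50% and 0.77 at 90%. An arbitrary f can therefore create an apparent departure or hide a real one.

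**Step 5: the fasting phrase.** Protocol 5.3.2 lists meal and dietary restrictions as not applicable, and the IV cohorts receive an infusion. The qualifier on dose has no counterpart in the design. It does not affect the fit.

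**The case against.** The strongest reply is that nothing is wrong with the inference. The slope, its SE and a valid 90% interval all follow from the identified total variance, and a competent programmer would see the redundant term and drop it. This stands for the theory, and it rules out a reading that a reader might be tempted by: that the interval has no defined degrees of freedom. It has N - 2.

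A reader might also infer that the interval will be grossly wide. Imposing 1 df would give 0.957 ± 6.314 × 0.02914, or 0.77 to 1.14. Neither document names a rule that gives 1 df, so this shows only how sensitive the interval is to the choice. SAP 14.5.1 names SAS but no procedure, the test fits used other software, and the shell for Table 3.03 is in a separate document not available here. The wrong standard errors are a possible numerical risk, not a prediction of the sponsor's output.

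A third inference would be that dose selection is undermined. The documents do not support that either. Protocol 9.1 sets no formal hypotheses for Part A. Escalation rests on the committee's review of safety and PK data (Protocol 4.3), and the Part B dose on observed PK and target-engagement data (Protocol 4.4.2).

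What remains is that the written specification cannot be fitted as stated, and that the SAP does not say how to resolve it.

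**Conclusion.** The model is mis-specified as written, at low severity. That the two variances cannot be separated follows from the single-dose design and needs no assumption. The slope estimate is unaffected, and the correct interval is the ordinary-regression one, on 28 df with 30 IV-active participants. The practical effect is limited to the reported 90% interval and the residual diagnostics for an optional, descriptive analysis, and whether it appears depends on the software and options used. The numerical illustrations rest on the assumed log-SD, weights and slope; the algebra does not.

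**What to change.** In SAP 9.1.5.1:

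- Delete the random subject term and define log α as a common fixed intercept with an independent residual error.
- State that the model is fitted by ordinary least squares to the active participants in the IV cohorts, separately for each endpoint.
- State that the slope is reported with a 90% t-interval on N - 2 degrees of freedom, where N is the number of participants with a value for that endpoint.
- State that the diagnostic plots use the residuals from this regression.
- Remove the fasting qualifier from the definition of dose.

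The cost is one SAP edit and a check that the shell and program for Table 3.03 match it. The model becomes simpler and no new data are needed. If the table has already been produced with the random term, refit it and compare the standard error and degrees of freedom.

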9.2.1. Endpoint / Variables

Blister concentrations of GSK3858279.

9.2.1.1. Drug Concentration Measures

Refer to [Appendix 5](#) (Section 14.5.3).

9.2.1.2. Derived Pharmacokinetic Parameters

Pharmacokinetic parameters will not be calculated due to the sparsity of blister fluid samples.

The within subject and timepoint blister fluid:serum concentration ratio for GSK3858279 may be determined from the concentration-time data if data permit.

9.2.2. Summary Measure

Individual and mean/median concentration-time profiles of GSK3858279 in blister fluid (stratified by treatment group) will be plotted and listed. Blister fluid concentrations will be summarized descriptively.

9.2.3. Population of Interest

The blister pharmacokinetic analyses will be based on the Blister Pharmacokinetic population, unless otherwise specified.

9.2.4. Strategy for Intercurrent (Post-Randomization) Events

Missing data would be considered as Missing at Random and no imputations for missing data would be carried out.

9.2.5. Statistical Analyses / Methods

Details of the planned displays are presented in [Appendix 11](#) and will be based on GSK Data Standards and statistical principles.

Unless otherwise specified, endpoints / variables defined in Section 9.1.1 will be summarised using descriptive statistics, graphically presented (where appropriate) and listed.

10. PHARMACODYNAMIC ANALYSES

10.1. Serum Target Engagement Analyses

The Target Engagement analyses described below will be carried out for Free and Total CCL17 in Serum.

10.1.1. Endpoint / Variables

Free and Total CCL17 levels in serum and derived Target Engagement parameters.

10.1.1.1. Target Engagement Concentration Measures

Refer to [Appendix 5](#) (Section 14.5.4).

10.1.1.2. Derived Target Engagement Parameters

10.1.1.2.1. Part A

All Target Engagement parameters in Part A will be determined directly from the observed concentration-time data, as data permits. All calculations will be based on actual sampling times.

Target Engagement parameters that will be calculated for free CCL17 in Part A are listed below. Additional parameters may be included as required.

CCI

NOTES:

Additional parameters may be included as required.

Target engagement parameters that will be calculated for total CCL17 in Part A are listed below. Additional parameters may be included as required.

CCI

NOTES:

Additional parameters may be included as required.

[figure not shown]
